
## SAMPLE SIZE

Studies in the literature have demonstrated that an increase in 6-minute walk distance of 37 meters is of clinical significance and can be observed with a 10% increase in left ventricular ejection fraction (EF) in patients with Class II-III NYHA (87). In the present study we expect that the baseline EF will be  $45\pm2\%$ . To observe at least a 10% increase in EF with an autocorrelation of 0.96 and an alpha = 0.05 and 90% power following  $\beta$ -OH-B infusion would require 23 subjects per group. With a 10% drop out rate, one needs to recruit 26 subjects per group ([name], Professor, Dept. of Biostatistics and Epidemiology, UTHSCSA).

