**Subjects:** 78 type 2 diabetic subjects with New York Heart Association (NYHA) Class II-III heart failure (75) and ejection fraction less than 45% (documented by patient's medical records with an ECHO or any other heart imaging study) will be studied. Other inclusion criteria include age = 18-80 years; BMI =23-38 kg/m^2; approximately 39 males/39 females; HbA1c = 5.5.0-10.0%; BP < 145/85 mmHg; eGFR > 30 ml/min•1.73 m^2. Subjects must be on a stable dose of guideline-directed heart fail medication (i.e. ACEI, ARB, ARNI, beta blocker, diuretic and/or mineralocorticoid receptor antagonist). Patients must be on stable antihypertensive therapy for at least 2 months. Only diabetic subjects treated with diet/exercise, metformin monotherapy, sulfonylurea monotherapy, low-dose (defined as  $\leq$  45 IU total daily dose) insulin therapy or combination metformin/SU/low-dose insulin therapy. Diabetic subjects treated with a GLP-1 RA or DPP4i (since they inhibit glucagon secretion) or pioglitazone (since it improves skeletal muscle and myocardial insulin sensitivity), SGLT2 inhibitor (since they increase plasma ketone concentration) or high-dose insulin will be excluded. Only subjects whose body weight has been stable ( $\pm$ 4 pounds) over the last 3 months will be studied. Subjects with contraindications for MRI procedures will be excluded, including patients with pacemakers. Women who are pregnant or breastfeeding will be excluded. All subjects with NY Heart Association Class II-III will be recruited from the Heart Failure Clinic at the University of Texas Health Science Center ([name] and [name]). Medical records for Cardiology and Diabetes clinics will be reviewed for eligibility and if potential participants meet inclusion/exclusion criteria they will be contacted about participating in the study. Collectively, these two clinics follow  $\sim$ 4,700 patients who have NYHA Class II-III and approximately 40% of these individuals have type 2 diabetes mellitus. The study will be approved by the UTHSCSA IRB and all subjects will provide written voluntary consent prior to participation.

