**Study Protocol:** Up to 100 Study participants will be asked to fast prior to consenting to the study and the day of the screening visit (day -30 to -7) participants will first sign consent form and eligibility criteria (A1c, eGFR, BP etc) will be confirmed and subjects will undergo a medical history and physical exam to exclude major organ system diseases other than diabetes and cardiac disease. Routine blood chemistries, CBC, urinalysis, lipid profile, TSH/T4, NT-proBNP, and EKG will be obtained. Blood pressure will be measured after reclining for 5 minutes in a quiet room and the mean of three measurements will be recorded. Subjects also will have a DEXA to measure total body fat content. If patient has not had an ECHO within 3-6 months of the screening visit, we will refer patient to the cardiac ECHO to confirm that the EF is < 50% (76).

Within 1-4 weeks after the screening visit, subjects will return to the Research Institute (RI) at 0700 h for a cardiac MRI (19,77) to confirm that the EF is < 50% and to obtain quantitative measures of baseline cardiac functional parameters: chamber volumes and pressures, wall thickness, LV diastolic function (E/A ratio, peak LV filling rate, diastolic volume) and LV systolic function (cardiac output, stroke volume, systolic volume, peak LV ejection rate). Strain and tagging also will be measured. To reduce the likelihood of hypoglycemia during the study procedures, subjects will be asked to withhold their antidiabetic therapy on the day of the studies until they have received a meal at the end of the study days.

Cardiac MRI will be performed by [name]. (Professor, Department of Radiology, UTHSCSA) on 3.0T MRI System (TIM, Trio, Siemens Medical Solution, Malvern, PA) with six channel anterior phased-array torso coil and corresponding coil elements (12 channels total) (19,77). Before cardiac MRI, catheters will be inserted into both antecubital veins for all blood withdrawal and  $\beta$ -OH-B infusion, respectively. Three blood samples will be drawn at 10-15 minute intervals for measurement of NT-proBNP, -OH-butyrate, acetoacetate,

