glucose, FFA, lactate, pyruvate, glycerol, HCO3, insulin, glucagon, renin and aldosterone. Axial and sagittal localizer views, standard two-, three-, and four-chamber views, with 7 mm thick slices are obtained using gradient echo sequence (2.2 x 1.3 mm^2 pixel). Cine imaging with retrospective gaiting is used with a balanced steady-state free precision sequence (TR/TE = 2.44/1.22 ms). Acquisitions consist of 25-30 cardiac phases, matrix 224 x 288, FOV 336 x 430 mm^2, 1.5 x 1.5 mm^2 pixel area. Contiguous short-axis slices are acquired during repetitive breath-holds at expiration. Mitral inflow images are obtained using phase-contrast gradient-echo (PCGE) sequence with through-plane velocity encoding (Venc = 100 cm/s) at the mitral valve with flip angle = 10° and TR/TE = 5.8/3.6 ms. PCGE slice thickness was 8 mm with typical FOV = 228 x 430 mm^2, matrix = 192 x 102, producing 2.89 x 2.89 x 8.0 mm pixel volumes.

Following completion of the baseline MRI, subjects will be divided into three groups (19 subjects per group). Each group will receive a 6-hour (3-hour in group III) prime-continuous infusion of racemic  $\beta$ -OH-B (100 mg/mL solution; pH adjusted to 7.4) to increase the plasma  $\beta$ -OH-B concentration by ~0.5, ~2.0, and ~5.0 mmol/L (43,74).

GROUP I: Prime = 0.4 mg/kg.min for 20 minutes and constant rate = 0.2 mg/kg.min until study end

GROUP II: Prime = 1.5 mg/kg.min for 20 minutes and constant rate = 0.75 mg/kg.min until study end

GROUP III: Prime = 4.0 mg/kg.min for 20 minutes and constant rate = 2.0 mg/kg.min until study end

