### **Myocardial Glucose Uptake: F-2-deoxyglucose/PET**

The same 19 diabetic subjects who received the  $\beta$ -OH-B infusion designed to raise the plasma  $\beta$ -OH-B concentration by 2 mmol/L (Group II) will receive a cardiac positron emission tomography (PET) study to examine the effect of hyperketonemia on myocardial glucose uptake and blood flow. The PET study will be performed with subjects lying comfortably in the scanner as previously described (19,78,79). Subjects will report to the Research Imaging Institute at 0700 following a 10 hour overnight fast. PET scans will be performed in two-dimensional imaging mode using ECAT 931-08/12 PET scanner (CTI, Knoxville, TN) with 10.5-cm axial field of view and resolution of  $8.4 \times 8.3 \times 6.6$  mm^3 full width at half-maximum. Point-of-care urine pregnancy test will be done for women of reproductive age prior to injection of radioisotopes. A catheter (for arterialized blood withdrawal) is placed in a vein on the dorsum of the hand, which rests in a box heated to 60°C, and three baseline blood samples are drawn at 15 minute intervals. A second catheter for infusion of test substances is inserted into an antecubital vein. Following optimization of subject position, a 20-minute transmission scan will be performed after exposure of a retractable 68Ge ring source to correct emission data for tissue attenuation of gamma photons. Then, O-water (10.5 MBq/kg) is administered intravenously through the catheter over 20 seconds at infusion rate of 10 ml/min and PET scan is performed to measure myocardial blood flow (MBF), as previously described (19,78,79).

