## Statistical Analysis

Data are expressed as mean  $\pm$  SD or as percentages. Statistical analyses will be performed using R 3.2.1 statistical software with RStudio IDE, Version 0.99.467. Paired, two-sided Student's t-test will be used to evaluate the null hypothesis of no difference between baseline and post  $\beta$ -OH-B butyrate protocol.  $p<0.05$  is deemed significant. Pearson's product-moment correlation will be used to examine the relationship between changes in parameters of LV diastolic and systolic function and coronary blood versus changes in myocardial  $\beta$ -OH-B uptake and both univariate and multivariate ANOVA for changes in EF in the 3 different  $\beta$ -OH-B infusion groups.

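### The 23 patients per group do not follow from the stated inputs, which give 2 or 3, and the group size is 19 in the procedures but 26 in the sample-size section

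*Combined protocol and SAP*

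**What the plan says.** The SAMPLE SIZE section sets the EF assumption ("In the present study we expect that the baseline EF will be" 45±2%) and the target ("To observe at least a 10% increase in EF with an autocorrelation of 0.96 and an alpha = 0.05 and 90% power following" the infusion). It concludes that this "would require 23 subjects per group. With a 10% drop out rate, one needs to recruit 26 subjects per group".

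The Statistical Analysis section names the within-group test: "Paired, two-sided Student's t-test will be used to evaluate the null hypothesis of no difference between baseline and post" infusion. It also says that data are reported as mean ± SD.

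The group size appears in four places:

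- Subjects paragraph: "78 type 2 diabetic subjects with New York Heart Association (NYHA) Class II-III heart failure (75) and ejection fraction less than 45"%, that is, 78 patients in total.
- SAMPLE SIZE: 23 completers and 26 recruited per group.
- Study Protocol: "Following completion of the baseline MRI, subjects will be divided into three groups (19 subjects per group").
- Myocardial Glucose Uptake section, for Group II: "The same 19 diabetic subjects who received the" middle infusion.

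On EF at entry, the Subjects paragraph requires less than 45% from medical records. The Study Protocol has patients return "for a cardiac MRI (19,77) to confirm that the EF is < 50"%, and applies the same 50% limit to the screening echocardiogram.

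**The concern.** A correlation of 0.96 between the two EF measurements, with an SD of only 2 points, makes the paired change very precise. A 10% rise would then be many SDs of change, and a requirement of 23 patients is far too large to have come from those figures. At least one of the SD, the effect or the correlation must differ from what was actually used.

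This matters because the section is the only quantitative support for the size of the trial. Expected Results raises the small groups as a limitation and answers it by pointing to this sample size, together with the reproducibility of MRI and PET. If the calculation cannot be reproduced, that answer cannot be checked.

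The conflict over group size adds to the problem. The 19 in the procedures is neither the 23 completers the plan says it needs nor the 26 it says it will recruit. Whether 19 would be enough depends on the SD of change, which the plan does not give.

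**Working it through.** **Inputs.** From SAMPLE SIZE: mean EF 45, ±2, a 10% increase, correlation 0.96, alpha 0.05, power 90%, 10% dropout. From Statistical Analysis: paired two-sided t-test; ± denotes SD. Assumption: equal SD before and after infusion. Power is exact, from the noncentral t distribution.

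**Steps that reproduce.** 23 / 0.9 = 25.6, rounded up to 26; 3 × 26 = 78, matching the Subjects paragraph.

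**The 23 itself.**

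SD of change = SD × √(2(1 − ρ)) = 2 × √(2 × 0.04) = 0.566 points.

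| Reading of 10% | Change (points) | Change / SD of change | Power at n = 2 | Power at n = 3 | n needed |
|---|---|---|---|---|---|
| Relative (10% of 45) | 4.5 | 7.95 | 0.62 | 0.9999 | 3 |
| Absolute | 10 | 17.7 | 0.95 | – | 2 |

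**Could another correlation explain it?** With SD 2 before and after and a 4.5-point change:

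- ρ = 0: SD of change 2.83; power 0.87 at n = 6 and 0.94 at n = 7, so n = 7.
- ρ = −1, the extreme: SD of change 4.0; n = 11 (power 0.92).

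No correlation brings n to 23 with an SD of 2.

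**Could ±2 be a standard error?** From 19, 23 or 26 patients the SD would be 2√n = 8.7, 9.6 or 10.2. With 0.96 kept, the SD of change is 2.47, 2.71 or 2.88. Then n = 6, 7 or 7 for 4.5 points, and 3, 4 or 4 for 10 points.

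**Could it be a between-group calculation?** SAMPLE SIZE gives no between-group effect. A three-group ANOVA with the stated SD or the implied SD of change needs 2 to 17 per group over the mean patterns tried (largest mean difference 2.25 to 10 points).

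**Working back from 23.** A paired test with n = 23 and 90% power detects 0.707 SD of change.

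- On the stated inputs: 0.707 × 0.566 = 0.40 EF points, or 0.40 / 45 = 0.9% relative.
- For a 4.5-point change: the SD of change must be 4.5 / 0.707 = 6.36. At correlation 0.96 that is an EF SD of 6.36 / √0.08 = 22.5, against the stated 2.

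**What the group size means for power.** 19 recruited less 10% leaves 17.

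| Completers | Detectable change (SDs of change) | Largest SD of change for 4.5 points at 90% power | Power if SD of change is 6.36 |
|---|---|---|---|
| 23 | 0.707 | 6.4 | 90% |
| 19 | 0.787 | 5.7 | 83% |
| 17 | 0.838 | 5.4 | 78% |

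The documents give no SD of change. Assumed values of 4, 5, 6 and 8 points need 11, 16, 21 and 36 patients for 4.5 points.

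**Totals.** 3 × 19 = 57 against 78: a difference of 7 per group, 21 overall.

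**The case against.** **A route to about 23 exists.** If ±2 is a standard error from 23 to 26 patients, 10% means 10 absolute points and the correlation is left out, the paired test needs 22 to 24 and a two-sample test 21 to 23. This may be where the figure came from. But it discards a stated input and conflicts with the plan's own mean ± SD convention. It therefore supports the point that the inputs used are not the inputs written.

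**Some inputs are interpreted.** SAMPLE SIZE does not label the ±2, does not name the test, and says autocorrelation rather than pre/post correlation. That is fair. The alternatives tried above cover these readings, and none that keeps all the stated inputs comes near 23.

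**The error is in the safe direction.** On the stated inputs 23 is far more than enough, and even 17 or 19 completers have about 100% power. This stands, and the point should not be read as a claim of low power. It does not restore the justification, because those inputs are evidently not the ones used.

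**The total is clear.** The plan states 78 outright, while 57 is only the product 3 × 19. This also stands: the 19 may be text left over from another calculation (17 / 0.9 = 18.9, rounded up to 19), though the documents do not say so. It is still the number in the current procedures for dividing the groups and for the PET study.

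**The EF limits are a side issue.** The baseline EF is most naturally the MRI value, whose limit is 50%, and a mean of 45 is compatible with that. This largely stands. A secondary tension remains with the 45% limit from records, since the plan also says that MRI and echocardiography agree closely.

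**Conclusion.** The concern holds. The stated inputs give 3 patients (relative reading) or 2 (absolute reading) for the planned test, against 23 in the plan. This rests on reading ±2 as an SD, reading 0.96 as the correlation between the baseline and post-infusion EF, and equal SDs at both times. Relaxing the correlation to its extreme gives at most 11, and reading ±2 as a standard error with the correlation kept gives at most 7.

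The group size is also inconsistent in current text: 19 per group in two places, 26 recruited per group and 78 in total in two others.

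The result is a sample size whose power cannot be known from the document, not one shown to be too small. If the SD of change were the 6.4 points needed to justify 23, a group of 19 would have 83% power, or 78% with 17 completers. The EF thresholds are a lesser matter that needs reconciling.

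**What to change.** 1. Re-run the calculation for the paired EF change. Give the SD of that change and its source, and say whether 10% is relative or absolute.
2. Report the detectable change at the planned number of completers. Suggested wording: 23 completers give 90% power for a mean change of 0.71 SD of the paired difference, that is X EF points with SD Y from [source].
3. Use one group size in the Subjects paragraph, the Study Protocol, the Myocardial Glucose Uptake section and SAMPLE SIZE. Recruiting 26 for 23 completers agrees with the total of 78. If 19 is kept, change the 78 and the 26, say whether 19 means recruited or completing, and report the detectable change (0.79 SD for 19 completers).
4. Reconcile the EF limits in the Subjects and Study Protocol paragraphs, and state a baseline mean and SD compatible with them, naming the measurement.

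The cost is one calculation and text corrections. Keeping 26 per group adds no patients to the stated 78; compared with the 57 implied by the procedures it is 21 more. Once the SD of change is sourced, the required number could itself change.
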